### 13.2.2 Primary Endpoint

The primary endpoint for efficacy is EFS6. The event-free interval begins with the date of diagnostic biopsy, and ends as described in Section 2.1.

### 13.2.3 Primary Analysis

The null hypothesis is that EFS6 is 50%. The alternative hypothesis is that EFS6 will be 65% or more. The figure of 65% is the minimum thought to indicate the treatment regimen is worthy of further study. We will construct an exact (Clopper-Pearson), one-sided (lower), 90% confidence interval about the observed EFS6. If that the lower limit of that confidence interval is greater than 0.5, the treatment regimen will be deemed worthy of further study.

### 13.3 Sample Size and Accrual Goal

The accrual goal is 30 evaluable participants. The table below shows the lower bound of the 90%, one-sided, exact confidence interval as a function of sample size and true proportion (precision = 0.14). As the table shows, given the true proportion EFS6 is at least 65%, then 28 observations from evaluable subjects have at least 90% probability to yield a lower, one-sided confidence bound that excludes the historical-control value of 50%. Our goal is 30 evaluable subjects to allow for unanticipated losses.

Sample Size (evaluable)	True Proportion	Lower Bound*
28	60%	46%
28	65%	51%
28	70%	56%

- Rounded so as to assure coverage

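### Section 13.3 claims at least 90% probability of success at a true EFS6 of 65%; the plan's own exact rule gives about 62% with 28 subjects and 51% with 30.

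*Combined protocol and SAP*

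**What the plan says.** Section 13.2.3 sets up a go/no-go test on EFS6. For the null it says "The null hypothesis is that EFS6 is 50" percent, and then: "The alternative hypothesis is that EFS6 will be 65% or more". It describes 65% as the smallest rate that would make the regimen worth pursuing. The analysis is "We will construct an exact (Clopper-Pearson), one-sided (lower), 90% confidence interval about the observed EFS6", and the decision rule is that if the "lower limit of that confidence interval is greater than 0.5, the treatment regimen will be deemed worthy of further study".

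Section 13.3 then justifies the sample size. Citing its table, it states that with a true EFS6 of at least 65%, "28 observations from evaluable subjects have at least 90% probability to yield a lower, one-sided confidence bound that excludes the historical-control value of 50" percent. The table has three rows, all at n = 28. They pair what is headed as the true proportion (60%, 65%, 70%) with a lower bound (46%, 51%, 56%), and the text gives a precision of 0.14. The accrual target is set slightly higher: "Our goal is 30 evaluable subjects to allow for unanticipated losses".

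**The concern.** The sentence in 13.3 describes the chance of meeting the decision rule at a given true rate, which is power. The table cited for it gives one lower bound per assumed proportion and no probability. At a true rate of 65% the expected count among 28 is 18.2, almost exactly where a bound of 51% just clears 50%. A design whose expected result sits at its own cut-off succeeds roughly half the time, not nine times in ten.

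This is the only probability of success the plan states, and the sample size rests on it. Someone relying on it would take a failed trial as strong evidence that EFS6 is below 65%. If the true figure is nearer 50% to 60%, a failed trial says much less.

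**Working it through.** **Inputs.** From 13.2.3: null rate 0.50, alternative 0.65 (power over the range of 65% or more is lowest at 65%), an exact Clopper-Pearson one-sided lower limit at 90%, and success if the limit is above 0.5. From 13.3: n = 28 for the claim and n = 30 as the goal. EFS6 is treated as a simple binomial proportion of evaluable subjects, as the plan does.

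**Step 1: reproduce the table.** The lower limit for x event-free subjects out of n is the 10th percentile of a Beta(x, n − x + 1) distribution. Put in x = 28 × proportion:

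| Proportion | x = 28 × proportion | Lower limit | Printed |
|---|---|---|---|
| 60% | 16.8 | 0.461 | 46% |
| 65% | 18.2 | 0.511 | 51% |
| 70% | 19.6 | 0.563 | 56% |

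The bounds reproduce, and 0.65 − 0.51 = 0.14 matches the stated precision. So the table gives the limit when the *observed* proportion equals the row value, although the column is headed as the true proportion.

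**Step 2: find the cut-off.** Take the smallest count r whose lower limit exceeds 0.5.

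- n = 28: 17 gives 0.468 (fails), 18 gives 0.504 (passes), so r = 18.
- n = 29: 18 gives 0.485 (fails), 19 gives 0.519 (passes), so r = 19.
- n = 30: 19 gives 0.49987 (just fails), 20 gives 0.534 (passes), so r = 20.

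**Step 3: compute power and type I error.** Power = P(X ≥ r) for X binomial(n, 0.65). Type I error = P(X ≥ r) for X binomial(n, 0.50). The last column is the true rate at which P(X ≥ r) = 0.90.

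| n | r | Power at 65% | Type I error | True EFS6 for 90% power |
|---|---|---|---|---|
| 28 | 18 | 61.6% | 9.2% | 73.3% |
| 29 | 19 | 56.2% | 6.8% | 74.3% |
| 30 | 20 | 50.8% | 4.9% | 75.2% |

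At a true rate of 65%, the chance of failing is 100 − 61.6 = 38.4% with 28 subjects and 100 − 50.8 = 49.2% with 30. Even at a true rate of 70%, power is 80.9% with 28 and 73.0% with 30.

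**Step 4: look for another reading that gives 90%.** At n = 28 and a true rate of 65%:

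- Wald, score and mid-P limits all keep r = 18, so power stays at 61.6%.
- The normal approximation gives 62.6%.
- A one-sided 80% level gives 75.3%, and a one-sided 95% level gives 46.1%.
- The chance that the observed proportion merely exceeds 0.5 is 92.6%, but that is not the rule in 13.2.3.

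**Step 5: scale.** Under the same rule, 90% power at 65% is first reached at n = 72 (r = 42, power 90.4%). Because counts are discrete, it dips below 90% at some larger n and holds throughout only from n = 79. These figures show the size of the gap; they are not a proposed sample size.

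**The case against.** Several points can be made for the plan.

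- **The claim is made for 28, not 30.** This is right. The direct contradiction is 90% against 61.6%. The 50.8% applies if all 30 targeted subjects are evaluable.
- **The figure for 30 is a quirk of discreteness.** This is also right: 19 of 30 misses by 0.00013, and a Wald, score or mid-P limit would pass it, giving 65.5%. But the plan specifies Clopper-Pearson and a limit above 0.5, so 50.8% is correct under the stated rule, and 65.5% is still far from 90%.
- **The alternative is 65% or more, so higher rates count.** A claim of at least 90% must hold across that whole range. With 28 subjects it fails from 65% up to about 73%.
- **The rest of the section is sound.** The bounds and the precision figure reproduce, and the type I error stays below the nominal 10%. The fault lies in the power sentence and the table heading.
- **This is a small phase II study meant to estimate.** That softens the consequence. However, 13.2.3 sets a binary rule for the primary endpoint, and the relaxed approach in 13.4.2.1 covers only secondary and ad-hoc analyses.

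Reading the 90% confidence level as a 90% chance of success is the likeliest origin of the error, but the documents do not say so. The conclusion does not depend on it.

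**Conclusion.** The power statement in 13.3 is wrong as written. At the plan's own 65%, the probability of success is 61.6% with 28 evaluable subjects, about 28 percentage points below the claim (90 − 61.6 = 28.4). With 30 it is 50.8%, about 39 points below (90 − 50.8 = 39.2). Raising the goal from 28 to 30 as an allowance for losses lowers the chance of success if no losses occur, and the plan does not say so.

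This rests on the rule exactly as stated in 13.2.3 and on every evaluable subject having a known status at six months. It needs no figure from outside the documents. Nothing elsewhere in the protocol corrects the sentence. Because it is the stated reason for the sample size, it should be corrected.

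**What to change.** Change Section 13.3 only:

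1. Replace the probability sentence with wording such as: *If true EFS6 is 65%, the probability that the one-sided 90% exact lower bound exceeds 50% is 62% with 28 evaluable subjects, 56% with 29 and 51% with 30. A probability of about 90% is reached when true EFS6 is about 73% (n = 28) or 75% (n = 30).*
2. Relabel the table column as the observed proportion. Since 16.8, 18.2 and 19.6 subjects cannot occur, either mark the rows as interpolated or replace them with attainable counts, for example 17/28 (limit 0.468) and 18/28 (limit 0.504).
3. Print the success cut-offs with their achieved one-sided type I error: 18/28 (9.2%), 19/29 (6.8%) and 20/30 (4.9%).

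The cost is a wording change and a less favourable stated power. No extra patients are needed, and the endpoint, the interval and the decision rule stay as they are.

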### 13.4 Other Analyses

#### 13.4.1 Description of Participants

Participants will be described by sex, age, and other host or clinical factors, using means, medians, and percentiles for continuous variables and counts and percentages for categorical variables. To the extent possible, participants will be compared to those who decline to participate in order to assess representativeness of the studied sample.

## **13.4.2 Analyses of Secondary Endpoints and Ad-Hoc Comparisons**

### **13.4.2.1 General Philosophy**

Consistent with the phase-ii nature of the project, we will examine the data in many ways to inform decisions about further research, including plots, tables, and statistical tests. Secondary analyses will be performed on intent-to-treat, per protocol, and ad-hoc data sets, as warranted. Given the total sample size of 28 to 30, probability values from statistical tests will be used as a guide to interpretation, which will also depend on clinical judgment. Therefore, we will not be concerned with overall, study-wise, type-1 error rates for secondary and ad-hoc analyses. As may be indicated, we will transform data to approach more closely analytic requirements, using logit transforms for percent data and log (for first choice) for continuous measures. If transformations fail, we will fall back on the analysis of ranks or use non-parametric methods.

### **13.4.2.2 Proportions**

Proportions, such as, overall remission rates and proportion who go to HSCT will be characterized by exact, binomial interval estimates and compared with Fisher's exact test.

### **13.4.2.3 Survival**

Time-to-event measures, such as, overall survival, time to normal hematopoiesis, duration of response, and influence of MRD status will be characterized by Kaplan-Meier methods, both overall and by strata of interest. Differences in times/survival between or among groups will be evaluated by the log-rank test. If assumptions are reasonably met, then Cox proportional-hazards models will be made to examine the effects on survival of covariates adjusting for other covariates. Ties in survival time will be broken by the subtracting a small, randomly generated amount from each tied observation (Borucka, 2014).

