## 2.2 Secondary Objectives/ Secondary Endpoints

2.2.1 Secondary Objectives	2.2.2 Secondary Endpoints

 
To evaluate any toxicities associated with the combination
 
	
 
Adverse events are to be captured and characterized by type, frequency, severity (as graded by NCI CTCAE v.5.0), timing, seriousness and relationship to study drugs
 

 
To evaluate the rate of response
 
	
 
The overall response rate (ORR) includes the rate of complete remission (CR) and complete remission with incomplete count recovery (CRi)
 

 
To evaluate the durability of response
 
	
 
Durability of response will be measured by relapse-free survival (RFS), defined as the amount of time a patient remains in remission after having achieved a CR or CRi
 

 
To evaluate survival and the length of survival
 
	
 
Survival follow up information will be collected to determine overall survival (OS)
 

 
To evaluate the time to return of normal hematopoiesis
 
	
 
Laboratory studies including complete blood counts (CBCs) will be collected to evaluate the recovery of bone marrow hematopoiesis
 

 
To evaluate the proportion of subjects who go on to receive allogeneic HSCT
 
	
 
HSCT information will be collected for patients who proceed to allogeneic HSCT
 

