### 5.3 Reinduction

Patients who are responding to the initial induction but not yet less than 5% blasts can receive a second induction. Patients who have not had any reduction in blasts count should be considered as refractory and should be considered for other treatment options off protocol. However, if there is a greater than 50% reduction in blast count but greater than 5% blasts present on marrow, re-induction is strongly recommended. The use of re-induction will be at the treating physician's discretion based on bone marrow biopsy performed on day 20 (+1 day). The regimen for re-induction will be CPX-351 at a dose of daunorubicin 44mg/m^2-cytarabine 100mg/m^2 on days 1 and 3. Glasdegib will be administered at 100mg daily on days 4-28. Reinduction can last longer than 28 days and up to 60 days. If reinduction last more than 28 days, patient should continue to take glasdegib daily and as prescribed until day 1 of next cycle of CPX-351. Patient will be instructed to hold glasdegib on the day they receive CPX-351 infusion.

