### **7.2 Procedures during Treatment**

#### **7.2.1 Induction**

- Physical exam will be done weekly
- Review previous and concomitant medications
- ECOG Performance Status Review
- Blood draws for laboratory studies will be done weekly
- ECGs will be done on day 6 before starting Glasdegib and approximately one week after day 6 (on day 13-15)
- Review of concomitant medications
- Adverse event assessment
- Assessment of minimal residual disease assessed by multi-parameter flow cytometry. This should be done according to local institutional guidelines.

- Bone marrow aspiration and biopsy
  - Day 20
  - Upon recovery of cytopenias typically around day 28 to 60, at the discretion of treating physician. If counts has not recovered by day 60, then complete on day 60.
- Additional BMA or PB will be collected for gene expression testing

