## **10.4 Event-free survival**

Event-free survival is defined as the time from screening biopsy to the date of confirmed disease progression, relapse from CR/CRi, treatment failure, or death, whichever comes first. This was chosen as an endpoint for several reasons. It is known to incorporate several endpoints of interest including efficacy of the treatment as well as toxicity that both contribute to the outcome of the patient. Complete remission may not capture the full benefits of Glasdegib since the drug may prevent relapse through different mechanisms than enhanced cytotoxicity.

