## **10.5 Final Response Assessment**

Overall survival is measured as the time from the date of diagnostic biopsy which confirmed disease to the date of death from any cause. Patients not known to have died at last follow-up are censored on the date they were last known to be alive. Patients will be followed for a minimum of one year from the completion of the treatment.

Patients who go on to allogeneic transplant will be censored for survival on the dates that they start conditioning regimen to avoid transplant as a confounding factor in analysis of overall survival.

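### Kaplan-Meier for time to normal hematopoiesis has no rule for death or other therapy before recovery, so under usual coding it would overstate the share who recover

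*Combined protocol and SAP*

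**What the plan says.** Section 13.4.2.3 covers several endpoints in one sentence: "Time-to-event measures, such as, overall survival, time to normal hematopoiesis, duration of response, and influence of MRD status will be characterized by Kaplan-Meier methods". Log-rank tests and, where assumptions allow, Cox models follow. No competing-event method appears.

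The recovery endpoint itself is given in Section 2.2.2 only as data collection: "Laboratory studies including complete blood counts (CBCs) will be collected to evaluate the recovery of bone marrow hematopoiesis". There are no count thresholds, no start date, no statement of who is analysed, and no rule for death or failure.

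RFS in Section 2.2.2 is "defined as the amount of time a patient remains in remission after having achieved a CR or CRi". Death is not named. Duration of response is listed in the Study Summary and in Section 13.4.2.3 but defined nowhere.

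Other endpoints are handled more fully. The EFS definition in Section 10.4 ends with "relapse from CR/CRi, treatment failure, or death, whichever comes first". Section 10.5 gives a censoring rule for overall survival, "Patients not known to have died at last follow-up are censored on the date they were last known to be alive", and a second one for transplant. Neither rule is extended to recovery, duration of response or RFS.

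**The concern.** A patient who dies while cytopenic can no longer recover. A patient who moves to other therapy can no longer recover because of the study regimen. Kaplan-Meier with these patients censored assumes that they would have gone on to recover at the same rate as those still under observation. One minus the curve then exceeds the proportion who actually recovered.

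The conduct of the trial makes such exits plausible before or during the recovery window, which Section 7.2.1 places as follows: "Upon recovery of cytopenias typically around day 28 to 60". The Study Schema footnote sends induction failures to follow-up. Section 5.3 says "Patients who have not had any reduction in blasts count should be considered as refractory" and points them to options off protocol, with the re-induction decision resting on the day-20 marrow. The Schedule of Events has hematology weekly in induction but only every 3 months in follow-up, so recovery after exit cannot be dated closely.

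Time to return of normal hematopoiesis is a named secondary objective. Section 1.5.3 reports prolonged cytopenias after CPX-351 in two trials, and Section 14.5.15 says that the toxicity of the combination is not well established. An optimistic recovery curve would weaken the information that this endpoint is meant to give.

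**Working it through.** The plan states no figure for these endpoints, so there is nothing to reproduce. The check asks how far 1 minus Kaplan-Meier (1-KM) departs from the true recovered share if deaths and exits are censored.

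**Inputs from the documents**
- n = 30 (Section 13.3).
- Recovery window about day 28 to day 60 (Section 7.2.1).
- p = 0.47 true recovery, using the CPX-351 CR/CRi rate in Section 1.5.3. This is a stand-in only: CRi, as defined in Appendix E, includes residual cytopenia.

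**Assumptions not in the documents**
- Recovery times uniform over days 28-60.
- A share d = 0.10 to 0.20 dies without recovery, uniform over days 5-60.
- A share q leaves for other therapy, uniform over days 20-60, where q is none, half or all of the remaining 1 - p - d.
- Everyone else stays at risk past day 60.

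**Formula (large sample)**
The fraction at risk during the window is Y(t) = 1 - p(t-28)/32 - d(t-5)/55 - q(t-20)/40, which is linear in t. Integrating the recovery hazard (p/32)/Y(t) from day 28 to day 60 gives

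1-KM(60) = 1 - [Y(60)/Y(28)]^k, with k = (p/32) / (p/32 + d/55 + q/40).

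**Worked cases**
- d = 0.10, q = 0: Y(28) = 0.958, Y(60) = 0.430, k = 0.890, so 1-KM = 51%.
- d = 0.20, q = 0: Y(28) = 0.916, Y(60) = 0.330, k = 0.802, so 1-KM = 56%.
- d = 0.10, q = 0.215 (half of 0.43): Y(28) = 0.915, Y(60) = 0.215, k = 0.671, so 1-KM = 62%.
- d = 0.20, q = 0.165 (half of 0.33): 1-KM = 67%.
- All non-recoverers leave by day 60: Y(60) = 0, so the large-sample value is 100%. Simulated trials of 30 average about 91%.
- d = 0, q = 0: Y(28) = 1, Y(60) = 0.53, k = 1, so 1-KM = 47%, with no bias.

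Simulation at n = 30 agrees with the formula in every case except the one where all leave.

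| Who is censored by day 60 | 1-KM, true 47% | 1-KM, true 60% |
|---|---|---|
| Nobody | 47% | 60% |
| Early deaths only (10-20%) | 51-56% | 65-72% |
| Early deaths plus half of the other non-recoverers | 62-67% | 76-81% |
| All non-recoverers | about 91% | about 96% |

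Timing matters too. If the deaths all fall before day 28 and nobody else leaves, 1-KM is 0.47/0.90 = 52% to 0.47/0.80 = 59%. Cumulative incidence with death and exit as competing events returns the true share in every row.

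**RFS and duration of response**
Here the open question is whether death in remission counts. Assume exponential times with an overall median of 6.9 months (the CPX-351 duration of remission in Section 1.5.3) and a share s of events that are deaths in remission (assumed). Censoring those deaths gives a median of 6.9/(1-s): 7.7, 8.6 or 9.9 months for s = 10, 20 or 30%. The 12-month estimate, 2^(-12(1-s)/6.9), rises from 30% to 34, 38 or 43%. This overstates durability, not recovery, and it vanishes if death is an event.

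**The case against.** Four points can be made on the other side.

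- **Censoring is not written.** Section 13.4.2.3 is silent. A reader might infer that the plan prescribes censoring deaths and failures; it does not. What stands is that a single-event Kaplan-Meier analysis with no other rule leads to that coding by default.
- **A large bias is not established.** A reader might take the 91% case as the expected result. It needs every non-recoverer to leave by day 60, and the documents point partly the other way. Induction may run to day 60 (Section 5.2), partial responders may have re-induction lasting up to 60 days (Section 5.3), and unrecovered patients have a marrow at day 60 (Section 7.2.1). Some exit is built into Section 5.3, but its share is unknown. This objection stands, and it is why the size is given as a range that includes zero.
- **RFS and duration of response may be distinct.** A reader might conclude that RFS as worded is the same endpoint as duration of response. That cannot be shown, because duration of response is never defined, and remaining in remission can be read as ending at death. What stands is that the wording leaves it open.
- **The endpoints are secondary.** Section 13.4.2.1 uses p-values only as a guide, and Section 13.4.2.2 reports remission rates as exact proportions beside any curve. That limits the harm. It does not correct a biased estimate of recovery, since a CR/CRi rate is not a count-recovery rate.

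**Conclusion.** The concern holds for time to normal hematopoiesis. The plan names Kaplan-Meier, gives no rule for death or other therapy before recovery, and under default coding the error can go only one way. At an assumed 47% true recovery the excess at day 60 is about 4-9 points if only 10-20% early deaths are censored (51-56 less 47), 15-20 points if half of the other non-recoverers also leave, about 44 points if all leave, and nil if all stay at risk past day 60. The exit share, the exit times and the use of CR/CRi for recovery are assumptions, so no single figure should be quoted.

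For RFS and duration of response the gap is one of definition and is secondary. The EFS6 decision does not depend on any of this. The change is worth making before analysis.

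**What to change.** In Section 13.4.2.3, estimate time to hematopoietic recovery in all treated patients by cumulative incidence (Aalen-Johansen), with death and subsequent therapy without recovery as competing events. State the start date and the count thresholds; the ANC and platelet values already used to date CR in Section 7.2.5 would serve. Log-rank and Cox comparisons can stay if described as cause-specific.

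As a secondary clarification in Section 2.2.2, state that death from any cause is an RFS event. Define duration of response separately and say how death in remission is handled. Give a transplant rule for both, because Sections 5.9 and 7.4 and Schedule of Events footnote M limit collection after HSCT to survival.

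The recovery change costs wording only: the software is standard and no new data are needed. The transplant rule needs a decision. Censoring or a competing event at transplant uses existing data, whereas counting relapse after transplant would require follow-up that is not now planned.
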